- **Diabetes:** American Diabetes Association classifies fasting blood glucose 100-125 mg/dL or HbA1c 5.7-6.4% as suggestive of impaired glucose tolerance (pre-diabetes). Similar to dyslipidemia, as fasting blood draws are not as commonly done in most primary care settings now for initial screening, for non-fasting (<8 hours) samples, blood glucose 140-199 mg/dL will be classified as suggestive of pre-diabetes if HbA1c was <5.7%. *Lifestyle intervention* is recommended (metformin prevention considered for select high risk populations).⁵⁴ Diabetes requires fasting blood glucose ≥ 126 mg/dL or HbA1c $\geq 6.5\%$. If not-fasting, random blood glucose ≥ 200 mg/dL would be concerning for diabetes if HbA1c was $<6.5\%$. In addition to lifestyle modifications, *metformin* is typically started with additional agents as indicated. We will ascertain the prevalence of pre-diabetes and diabetes; both may be eligible for Aim 2.

Undertreatment defined for each as:

- While any participant who was previously undiagnosed is also technically undertreated, we will reserve this definition to those who previously or currently reported to CCSS as being diagnosed with hypertension, dyslipidemia, or diabetes (either managed by lifestyle modifications or medication therapy), if their home-sampled value falls outside the recommended therapeutic range: blood pressure $\geq 130/80$ mmHg, LDL ≥ 160 mg/dL, triglyceride ≥ 150 mg/dL (if fasting <10 hours: ≥ 200 mg/dL), or HbA1c $\geq 7.0\%$ (different than the HbA1c diabetes diagnosis threshold⁶⁵).

3.3.2 **Primary Aim 2 Endpoint:** Probability of intervention subjects having an undertreated CV condition compared with the control group at 1-year follow-up.

3.3.3 **Primary Aim 3 Endpoint:** Barriers among survivors and their primary healthcare providers that contribute to undertreatment of hypertension, dyslipidemia, and diabetes.

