5.0 SUBJECT ELIGIBILITY

5.1 Inclusion Criteria

For Primary Aim 1:

- 5.1.1 CCSS participant who is age ≥ 18 years at time of initial consent.
- 5.1.2 High CV risk status based on CCSS risk prediction models for cardiomyopathy and ischemic heart disease.
- 5.1.3 Living in the U.S., within 50 miles of a designated exam service provider (e.g., EMSI) based on CCSS's available contact information at the time of approach.
- 5.1.4 Able to read, write, and speak English.
- 5.1.5 Ability to understand and the willingness to provide informed consent.

For Primary Aim 2, in addition to the satisfying the above criteria, participants must also meet the following criteria:

5.1.6 Abnormal CV condition identified on home visit. Defined as having at least one of the following:

- Average blood pressure $\geq 130/80$ mmHg ($\geq 130/80$ if existing hypertension diagnosis)
- LDL ≥ 160 mg/dL
- Triglyceride ≥ 150 mg/dL (if ≥ 10 hours fast) or ≥ 200 mg/dL (if < 10 hours fast)
- If not known to be diabetic: Glucose ≥ 100 mg/dL (if ≥ 8 hours fast) or ≥ 140 mg/dL (if < 8 hours fast)
- HbA1c $\geq 5.7\%$ (if not known to be diabetic), HbA1c $\geq 7\%$ (if known diabetic).

5.1.7 Be free of any known (self-reported) ischemic heart disease or cardiomyopathy.

5.1.8 Have access to a telephone or computer to receive a phone or web video counseling/intervention session at baseline and at 4 months.

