8.2 First Home Visit

This will include:

- Signature on HIPAA authorization and Medical Record Release form (optional).
- Standing height: in centimeters, to the nearest 0.1 cm.
- Weight: in kilograms, to the nearest 0.1 kg.
- Blood pressure at rest: 3 times; each at least 3 minutes apart.
- Waist circumference: in centimeters, to the nearest 0.1 cm; just above the uppermost lateral border of the right ilium [hip bone]; at the end of a normal expiration.
- Blood draw (no fasting required): lipid profile, blood glucose, hemoglobin A1c, insulin, and samples for ancillary biological studies (**Table 5**).

TABLE 5. Overview of blood samples, draw order, vial type, volume.

Draw order / Analyte	Vial type	Volume
1) Lipid profile, glucose, insulin level*	Heparin plasma separator tube (green top)	3.0 mL
2) Hemoglobin A1c*	EDTA tube (lavender top)	1.0 mL
3) Protein & DNA-based assays	EDTA tube (lavender top)	7.5 mL
4) General chemistries	Serum separator tube (red/gray top)	7.5 mL
5) Proteomics, metabolomics	EDTA separator tube (pearl)	7.5 mL
6) RNA for gene expression	PAXgene tube	2.5 mL

*These also will be drawn at the 2nd home visit; remaining tubes would NOT be drawn at the 2nd home visit unless they could not be successfully drawn at the first visit. 2nd home visit only: blood spot offered for failed venous draws.

With our 7/2020 protocol modification, in response to the unexpected closure of the study's original exam service provider (EMSI), replacement service providers may include those that do not provide home-based services but rather fixed laboratory / service centers that the participant travels to in order to obtain the specified research blood draw. In these instances, only tubes 1-2 (**Table 5**) will be drawn and processed on-site (i.e., tubes 3-6 will not be drawn).

Rarely, in past experiences with our pilot data and similar CCSS home visit-based studies, exam service staff will be unsuccessful in obtaining blood given technical issues. In this situation, the participant will be offered the choice of having the procedure be rescheduled to another date. *If the participant refuses and the primary study endpoints (lipid profile, blood glucose, and hemoglobin A1c) cannot be collected, then the patient will not be eligible to continue on the study.* Any partial results will still be sent back to the participant and their designated primary care provider.

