8.7 Second Questionnaire and Home Visit

The 2nd questionnaire and home visit should take place approximately 1-year after the initial questionnaire and home visit. The study will send participants an abridged version of the baseline questionnaire (by mail, with phone/email follow-up as necessary) with a reminder that a 2nd home visit is also due soon. After the participants complete the follow-up questionnaire, the study will work with the exam service provider to contact the participant to arrange for the 2nd home visit. The study will attempt to have all 2nd home visits occur within 3 months of the 1-year anniversary, and visits that occur outside that 3-month window will be flagged (but remain eligible for analysis). The following outcomes will be measured at this time point:

- Same physical measurements as before: standing height, weight, blood pressure at rest (3 times), and waist circumference.
- Blood draw (no fasting required): lipid profile, blood glucose, hemoglobin A1c, and insulin (**Table 5**; other assays will not be drawn unless they could not be drawn at the first home visit).
- If the exam service provider is unsuccessful in obtaining blood due to a technical issue, or the participant refuses the venous blood draw at the second visit, we will offer the participant the option of a finger poke to obtain a blood spot sample (i.e., dried blood spot, DBS). Blood spots will only be offered as a back-up option at the second visit.
- Handling of any critical results will be conducted similarly as per the baseline home visit (see **Section 8.5** above). In contrast to venous samples, DBS-based measurements of the lipid profile, glucose, insulin, and hemoglobin A1c will not be released back to participants or their providers. This is because such measurements are not performed in a CLIA-certified setting and are currently designed for epidemiologic research only (and not for clinical care), and also will be batched (in contrast to venous samples which are processed in near real-time).

Should home visits be completely declined or impossible to conduct (e.g., due to COVID-19 or other public health issues where social distancing is encouraged/mandated), the protocol will permit

substitution of a completely remote assessment procedure for the follow-up visit. This would necessarily be slightly modified from the exam service provider-obtained home visit in the following ways:

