Secondary analyses: In case survivors who were newly diagnosed (i.e., underdiagnosed) following their 1st home visit differ in their response to the intervention vs. those previously diagnosed but undertreated, we will examine estimates stratified by diagnosis status at the 1st home visit. For similar reasons, we also will examine estimates if pre-diabetes are excluded. In our primary model, we also will explore whether differences vary by sex, current age, time since cancer diagnosis, obese (BMI ≥ 30 kg/m²) vs. not, health insurance vs. not, and recent history of being seen in a dedicated long-term follow-up clinic for survivors vs. not. We also will explore, among intervention participants, whether action plan scores from the 4-month session are associated with differential undertreatment rates (as a single parameter). Finally, we plan to also compare across the study arms, the measured CV risk factor values from the 2nd home visit separately: 1) average systolic pressure, 2) average diastolic pressure, 3) LDL, 4) triglyceride, 5) blood glucose, and 6) HbA1c. For this subanalysis we will use linear models, adjusting for the value at the 1st home visit as a covariate.

Sample size considerations: Assuming 60% of Aim 1 participants (n=800) meet Aim 2 eligibility with a subsequent conservative 20% drop-out rate, ~380 survivors (190/arm) would have complete data. The study would be 80% powered ($\alpha=0.05$) to detect RRs ≤ 0.88 (i.e., $\geq 12\%$ reduction in the intervention vs. control group) if the prevalence of having an undertreated CV risk factor among controls after the 2nd home visit was 90% (10% reduction from baseline). If controls had an unlikely 50% reduction, we can still detect RRs ≤ 0.71 . Analyses stratified by initial underdiagnosis or undertreatment status (~75-150/arm) will be able to detect RRs ≤ 0.79 to ≤ 0.86 , respectively. Systematic reviews have reported RRs 0.6-0.8 for strategies similar our proposed interventions in the general population.^{64,65} For continuous outcomes (secondary analyses), we will be powered to detect change equaling $\sim 30\%$ of 1 standard deviation, which equates to 5 mmHg systolic blood pressure, 3 mmHg diastolic pressure, 10 mg/dL LDL, 30 mg/dL triglyceride, 10 mg/dL glucose, and 0.3% HbA1c. Differences within these ranges have been reported by others for interventions conducted in the general population.⁶⁶⁻⁶⁸

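### The secondary linear models for triglyceride and blood glucose take no account of fasting state, although neither visit requires fasting and the plan's own cut-points for both analytes depend on it

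*Combined protocol and SAP*

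**What the plan says.** The secondary analyses in section 13.2 compare six measured values from the 2nd home visit between arms. After the two blood pressures these are "3) LDL, 4) triglyceride, 5) blood glucose, and 6) HbA1c". The method is given in one sentence: "For this subanalysis we will use linear models, adjusting for the value at the 1st home visit as a covariate". Neither 13.2 nor any other section adds fasting state to these models as a covariate, stratum, restriction or sensitivity analysis.

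Fasting is optional at both draws. Section 8.2 (first visit) has "Blood draw (no fasting required): lipid profile, blood glucose, hemoglobin A1c, insulin, and samples for ancillary biological studies", and section 8.7 (second visit) has "Blood draw (no fasting required): lipid profile, blood glucose, hemoglobin A1c, and insulin".

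For classification, the plan treats meal timing as material. Section 5.1.6 has "Triglyceride ≥ 150 mg/dL (if ≥ 10 hours fast) or ≥ 200 mg/dL (if < 10 hours fast" for triglyceride and "Glucose ≥ 100 mg/dL (if ≥ 8 hours fast) or ≥ 140 mg/dL (if < 8 hours fast" for glucose in participants not known to be diabetic. At the diabetes level, section 3.3.1 uses 126 mg/dL fasting, and for other samples "If not-fasting, random blood glucose ≥ 200 mg/dL would be concerning for diabetes". Table 6 in section 8.5 follows the same split. The binary primary endpoint in 13.2 also uses fasting-specific cut-points.

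**The concern.** The plan cannot apply its cut-points without knowing, for each draw, whether the participant had fasted 10 hours (triglyceride) or 8 hours (glucose). Yet the linear models treat a fasted and a fed value as the same quantity. A survivor may be fasted at one visit and fed at the other, so adjusting for the 1st-visit value does not remove the problem. That covariate is itself a mixture of the two states.

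The stake is the precision of two secondary comparisons for which 13.2 makes explicit power claims: 30 mg/dL for triglyceride and 10 mg/dL for glucose. The gaps between the plan's own cut-points, 50 and 40 mg/dL, are larger than both. These models also carry some weight. Section 3.1.2 words Aim 2 as a comparison of changes in the measured values, and they are the only planned analyses that compare those values directly.

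**Working it through.** **Inputs from section 13.2.** 190 per arm with complete data, 80% power, α = 0.05 (sidedness is not stated; two-sided assumed), and detectable differences of about 30% of 1 SD, given as 30 mg/dL triglyceride and 10 mg/dL glucose.

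**The plan's figure.** (1.960 + 0.842) × √(2/190) = 0.287 SD, which rounds to the stated 30%. At exactly 0.30 SD the power is 0.83. The figure reproduces.

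**Implied SDs.** Triglyceride 30/0.30 = 100 mg/dL; glucose 10/0.30 = 33.3 mg/dL.

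**Cut-point gaps.** Triglyceride 200 − 150 = 50 mg/dL. Glucose 140 − 100 = 40 mg/dL, and 200 − 126 = 74 mg/dL at the diabetes level. LDL has one cut-point, 160 mg/dL, so its gap is 0.

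**Assumptions, not in the documents.** Half of the 2nd-visit draws are non-fasting (f = 0.5). The mean fed-minus-fasted shift d is 25-50 mg/dL for triglyceride and 10-40 mg/dL for glucose. The upper ends are the threshold gaps, which are not measured mean shifts.

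**If the implied SDs apply within one fasting state.** Mixing the states adds variance f(1 − f)d² = 0.25d². Power is about Φ(Δ/SE − 1.96), with SE = SD × √(2/190).

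| Outcome (Δ) | Shift d | Added variance | Share of implied variance | SD | Power |
|---|---|---|---|---|---|
| Triglyceride (30) | 0 | 0 | 0 | 100 | 0.83 |
| Triglyceride | 25 | 156 | 2% | 100.8 | 0.83 |
| Triglyceride | 50 | 625 | 6% | 103.1 | 0.81 |
| Glucose (10) | 0 | 0 | 0 | 33.3 | 0.83 |
| Glucose | 10 | 25 | 2% | 33.7 | 0.82 |
| Glucose | 40 | 400 | 36% | 38.9 | 0.71 |

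For glucose at d = 40, for example: SD = √(1111 + 400) = 38.9, SE = 38.9 × √(2/190) = 3.99, 10/3.99 = 2.51, and Φ(2.51 − 1.96) = 0.71. The detectable difference rises from 9.6 to 11.2 mg/dL.

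With only 10% non-fasting and the full threshold gaps, power is 0.82 for triglyceride and 0.79 for glucose.

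**If the implied SDs already contain the mixture.** The stated power then already carries this noise, and adjusting for 2nd-visit fasting would be a gain. At f = 0.5 and the upper shifts, the SD falls to √(10000 − 625) = 96.8 for triglyceride (power 0.86) and √(1111 − 400) = 26.7 for glucose (power 0.96).

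**Bias, only if fasting differs by arm.** The false difference is d times the difference in fasting share. A 10-point difference (assumed) gives 0.10 × 40 = 4 mg/dL for glucose and 0.10 × 50 = 5 mg/dL for triglyceride at the upper shifts. At a 10 mg/dL glucose shift it is 1 mg/dL, and the two-sided type I error is about 6%. With a 5-point difference and the full 40 mg/dL, the error is 9-10% (baseline correlation 0 to 0.5). With no difference between arms it stays at 5%.

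**The case against.** The strongest reply is that this concerns one sentence about a secondary subanalysis, that both arms have the same no-fasting rule and are allocated 1:1, and that visit staff are blinded, so meal timing is noise shared by both arms. The loss for triglyceride is negligible, and the glucose loss is large only when a threshold gap stands in for a mean shift. HbA1c remains as a separate glycaemic outcome. The source of the implied SDs is not stated, so the power claim may already allow for mixed states. All of this stands, and it limits the point to a modest one.

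The caution about adjustment also stands. Fasting at the 2nd visit is observed after randomisation. If the intervention changed it, adjusting for it, or restricting to participants with the same state at both visits, would condition on an effect of the arm and sit poorly with the intent-to-treat analysis in 13.2.

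Three stronger readings are tempting but lack support:

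- **LDL is affected too.** The plan uses 160 mg/dL whatever the fasting state and gives no figure for a shift, so nothing in the documents brings LDL in.
- **The primary endpoint is distorted.** It already uses fasting-specific cut-points. Whether a fed triglyceride passes more easily than a fasted one depends on the true fed-to-fasted ratio: at the plan's own 200/150 = 1.33 the two cut-points are equivalent, and the direction reverses on either side of that value.
- **The comparison is biased, with substantial type I error.** A large error needs both an assumed 10-point difference in fasting between arms and the full 40 mg/dL shift. Participants are unblinded and only one arm is counselled before the 2nd visit (sections 7.2 to 7.4), so a difference is possible, but the documents give no evidence of one.

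**Conclusion.** The omission is real for triglyceride and blood glucose in the secondary linear models, and for nothing else in the plan. It is a minor weakness, chiefly a matter of precision for glucose. The loss of power, at worst 0.02 for triglyceride and up to 0.12 for glucose, rests on the assumed share of non-fasting draws, on the assumed shifts, and on reading the implied SDs as within-state. The 0.12 also takes the cut-point gap as the mean shift, so it is an illustrative upper end and not an estimate. Bias remains a conditional possibility that a simple table by arm would let readers check.

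**What to change.** In the secondary analyses of section 13.2, for triglyceride and blood glucose only:

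1. Add fasting state at the 1st visit to the planned model beside the 1st-visit value, using the 10-hour category for triglyceride and the 8-hour category for glucose. It is a baseline variable and raises no post-randomisation issue, but it improves only the baseline adjustment.
2. Tabulate fasting state at the 2nd visit by arm.
3. Prespecify a sensitivity model that also adjusts for 2nd-visit fasting state, and report it beside the model without that term. This is the step that addresses meal-related noise in the outcome.

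The cost is a few lines of plan text, one table and one extra model per analyte. No new data should be needed, because the cut-points already require fasting status at each draw. The downside is that 2nd-visit fasting is measured after randomisation, so the estimate in step 3 is supportive and should not replace the main one. The models for LDL, HbA1c and blood pressure, and the binary primary endpoint, need no change on this account.

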7.4 Delayed Intervention Control

Survivors in the control arm will receive a copy of clinically meaningful baseline home visit results, with a general recommendation to seek medical follow-up in instances where any of those values are abnormal since we consider it unethical to withhold such information. A copy also will be sent to their designated healthcare provider. *As such, the control group's health may be improved simply by study participation.* At 4-months, participants will receive a generic thank you letter by mail for participating. This will include a reminder of the 2nd home visit, and to enhance control group retention, control participants will be told that they can receive the study intervention (minus the 4-month booster session) after completing the 2nd home visit and any associated surveys. This will include reviewing an SCP and self-management strategies with the study clinician, but we will avoid using those exact terms to minimize control group contamination.

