13.0 STATISTICAL CONSIDERATIONS

13.1 Aim 1 Analytic Plan

Hypothesis: Approximately 60% of participants will have an abnormal CV risk-factor finding that meets clinical intervention thresholds, and among those with abnormalities, 40% will be undertreated and 80% newly diagnosed.

Primary analyses: We will calculate the prevalence of hypertension, dyslipidemia, and diabetes by self-report and by physiologic measurement. We will then calculate the proportions (with exact 95% confidence intervals) of participants who may be underdiagnosed as well as the proportions undertreated (like **Figure 3**). We will calculate the prevalence of directly measured pre-diabetes separately. **Secondary analyses:** We will examine whether rates differ by: sex; current age; time since cancer diagnosis; obese ($BMI \geq 30 \text{ kg/m}^2$) vs. not; health insurance vs. not; recent history of being seen in a dedicated long-term follow-up clinic for survivors vs. not; and lifestyle factors (smoking, low fruit/vegetable intake, low physical activity).

Sample size considerations: Based on prevalence estimates from CCSS surveys and our pilot (**Table 2, Figure 3**), we expect ~60% of high CV risk participants ($n \sim 480$) to have an abnormal CV risk factor measurement; prevalence of individual risk factors ranging 20-40% (less when stratified by underdiagnosis/undertreatment status). With an overall sample $n=800$, we expect reasonable precision for our primary prevalence estimates (**Table 9**). Power to detect differences <10% in secondary analyses may be more limited.

TABLE 9. Estimated power for Aim 1 analyses.		
Prevalence \pm 95% CI	Minimum detectable proportions*	
N=800	N=320:480	N=200:200
5% \pm 1.5%	5% vs. 1/11%	5% vs. 0/14%
20% \pm 2.8%	20% vs. 12/29%	20% vs. 10/33%
50% \pm 3.5%	50% vs. 40/60%	50% vs. 36/64%

*2-sample Fisher's exact test, 80% power, $\alpha=0.05$.

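### The 80% power for RR 0.88, and the two stratum figures, rest on an unsourced and optimistic 90% of controls staying out of range; the likelier range below it is not shown

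*Combined protocol and SAP*

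**What the plan says.** The sample size text in section 13.2 assumes that 60% of 800 Aim 1 participants "meet Aim 2 eligibility with a subsequent conservative 20% drop-out rate", so that about "380 survivors (190/arm) would have complete data". It states 80% power at alpha 0.05 for a risk ratio of 0.88 or lower "if the prevalence of having an undertreated CV risk factor among controls after the 2nd home visit was 90% (10% reduction from baseline"). Baseline is 100% by construction, because everyone randomised has at least one out-of-range value.

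A second scenario follows: "If controls had an unlikely 50% reduction", the detectable risk ratio is 0.71. Analyses stratified by underdiagnosis or undertreatment, with about 75 to 150 per arm, are said to detect 0.79 to 0.86; no control prevalence is given for these. The text then cites risk ratios of 0.6 to 0.8 for similar strategies.

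Entry to the trial (section 5.1) requires "Abnormal CV condition identified on home visit", with no confirmatory visit. Section 7.4 has controls and their providers receive the results and concedes that the control group's "health may be improved simply by study participation". Section 13.1 expects "prevalence of individual risk factors ranging 20-40"%.

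**The concern.** Survivors are selected because a value exceeded a cut-point at one visit. The primary outcome asks whether values exceed largely the same cut-points at a second visit. Part of any single reading is within-person variation, so some survivors will be back in range with no change in health. Returned results and advice to seek follow-up can only add to that. The plan's 10% fall has to cover all of this, yet section 13.2 neither gives a source for it nor mentions regression to the mean.

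The stake is how small an effect the trial can reliably find. With the sample fixed, the detectable risk ratio moves away from 1 as control prevalence falls. The plan shows one favourable value, 90%, and one value it regards as unlikely, 50%. A reader cannot tell what the trial can detect in between.

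**Working it through.** **Inputs from the documents.** Evaluable sample: 800 × 0.60 × 0.80 = 384, or 192 per arm, rounded by the plan to 190. Allocation 1:1 (section 7.2). Power 80%, alpha 0.05, control prevalence 90% or 50%, strata of 75 and 150 per arm (section 13.2). Single-factor prevalence 20–40% (section 13.1). Aim 2 names no test; I use the two-sided Fisher's exact test that Table 9 names for Aim 1.

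**Reproducing the plan.** With control proportion p, the intervention proportion is RR × p. Power is the sum of the two binomial probabilities over all outcome pairs with Fisher p ≤ 0.05.

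- 190 per arm, 90% vs 0.88 × 90% = 79.2%: power 80.5%
- 190 per arm, 50% vs 0.71 × 50% = 35.5%: 79.5%
- 75 per arm, 90% vs 0.79 × 90% = 71.1%: 79.7%
- 150 per arm, 90% vs 0.86 × 90% = 77.4%: 81.1%

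All four stated figures reproduce. The last two do so at 90%, so the stratum figures carry that assumption without saying so.

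**How plausible is 90%? (illustration, assumed inputs)** Take three independent normal markers with prevalences 20, 30 and 40%, no true change, and the same correlation r between visits for each. The share eligible is 1 − 0.8 × 0.7 × 0.6 = 66.4%, near the plan's 60%. Among those eligible:

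| r (assumed) | A qualifying condition still out of range | Any condition out of range |
|---|---|---|
| 0.6 | 67% | 77% |
| 0.7 | 73% | 80% |
| 0.8 | 78% | 83% |
| 0.9 | 85% | 88% |
| 0.95 | 90% | 91% |

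The two columns reflect two readings of the endpoint: only conditions present at entry count, or any condition counts. In this set-up, 90% with no improvement at all needs r of about 0.95.

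**Power at 190 per arm if control prevalence is lower (assumed values, Fisher).**

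| Control prevalence | RR 0.88 | RR 0.8 | RR 0.7 |
|---|---|---|---|
| 90% | 80.5% | 99% | >99% |
| 85% | 66% | 97% | >99% |
| 80% | 54% | 92% | >99% |
| 70% | 37% | 78% | 98% |
| 60% | 26% | 61% | 92% |

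The pooled normal approximation is slightly more favourable for RR 0.88: 83% at 90%, then 58, 41 and 29% at 80, 70 and 60%.

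**Risk ratio detectable with 80% power (Fisher).**

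| Control prevalence | 190 per arm | 150 per arm | 75 per arm |
|---|---|---|---|
| 90% | 0.88 | 0.86 | 0.79 |
| 80% | 0.835 | 0.81 | 0.72 |
| 70% | 0.795 | 0.77 | 0.67 |
| 60% | 0.75 | 0.725 | 0.61 |
| 50% | 0.71 | 0.67 | 0.54 |

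**Value of baseline adjustment.** In the same set-up, predicting whether each qualifying condition persists from its type and first-visit value explains R² = 8.5, 11 and 15% of the outcome variance at r = 0.6, 0.7 and 0.8. The efficiency gain, 1/(1 − R²) − 1, is about 9, 13 and 17%, so roughly 10–20%.

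**The case against.** The strongest defence is that nothing is miscalculated and much is disclosed. The plan gives a far more pessimistic scenario than 90%, and every overall detectable risk ratio between 60% and 80% control prevalence (0.75 to 0.835) lies inside its own bracket of 0.71 to 0.88. It says openly that controls may improve. Most of the effects it cites stay detectable: RR 0.7 has at least 92% power down to 60% control prevalence. All of this stands.

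The inputs to the illustration can also be challenged. The 20–40% prevalence comes from pilot work that appears to have used a wider blood pressure threshold of 130/85, while entry and outcome now use 130/80; a lower diastolic cut-point would raise prevalence and persistence. Planned oversampling of rarer known conditions is not modelled. Table 6 drops the highest systolic reading and averages the other two, which reduces noise within a visit but not between visits. These points also stand, and are why the persistence figures are only an illustration.

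A reader might go further and infer that regression to the mean alone takes controls to 60–80%, so that the trial has 30–60% power for RR 0.88. The documents do not support that as a fact: they contain no test-retest correlation, within-person variance or persistence rate. Nor does 90% require a correlation of 0.97–0.98. That holds for a single condition at 20–40% prevalence, whereas the plan's 90% is per person, where about 0.95 suffices. Finally, the illustration does not reach a 50% fall, so it gives no reason to strike the plan's description of that scenario as unlikely.

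**Conclusion.** The concern holds as one about an assumption. The 80% power for RR 0.88, and the stratum values 0.79 and 0.86, are computed correctly but depend on 90% of controls remaining out of range. That value is unsourced and sits at the optimistic end, given single-visit selection and the return of results to controls and their providers.

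If control prevalence were 80, 70 or 60%, the detectable risk ratio would be about 0.835, 0.795 or 0.75 rather than 0.88. The mild end of the cited effects (0.8) falls below 80% power at 70% and lower. The documents do not support reading this as a trial underpowered for every effect it cites.

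Three assumptions limit the conclusion. The control prevalences are assumed, not documented. The 67–83% persistence rests on independent normal markers, a correlation of 0.6–0.8 and no true change. Every power figure treats the outcome as one yes/no result per person, while the primary analysis is a GEE over up to three outcomes, whose power may differ.

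**What to change.** In section 13.2:

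1. Present 90% as the optimistic case, or give its source.
2. State that the stratum figures 0.79 and 0.86 also assume 90%.
3. Tabulate the detectable risk ratio for control prevalence from 50 to 90%, overall and at 75 and 150 per arm. The last detectable-RR table under the working can serve, with a note that it uses one binary outcome per person. The 50% scenario and its wording may stay.
4. Pre-specify that the primary GEE adjusts for condition type and for the first-visit value of each contributing condition. The secondary linear models already adjust for the first-visit value.

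The cost is less favourable stated figures and some SAP wording. No participants, visits or measurements are added, since the first-visit values are already collected. The adjustment recovers some precision (about 10–20% in efficiency under the assumed correlations), but it does not restore the 0.88 headline if control prevalence is well below 90%.
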